Appendix 4. Allergic Reaction Toxicity Grading

Current NCI-CTCAE v. 4.03 grading system for allergic reactions defined as a disorder characterized by an adverse local or general response from exposure to an allergen.

Grade 1 - Mild	Grade 2 - Moderate	Grade 3 – Severe	Grade 4 – Life- threatening	Grade 5 - Death
Transient flushing or rash, drug fever <38 degrees C (<100.4 degrees F); intervention not indicated	Intervention or infusion interruption indicated; responds promptly to symptomatic treatment (e.g., antihistamines, NSAIDS, narcotics); prophylactic medications indicated for <=24 hrs	Prolonged (e.g., not rapidly responsive to symptomatic medication and/or brief interruption of infusion); recurrence of symptoms following initial improvement; hospitalization indicated for clinical sequelae (e.g., renal impairment, pulmonary infiltrates)	Life-threatening consequences; urgent intervention indicated	Death

Current NCI-CTCAE v. 4.03 grading system for anaphylaxis reactions defined as a disorder characterized by an acute inflammatory reaction resulting from the release of histamine and histamine-like substances from mast cells, causing a hypersensitivity immune response. Clinically, it presents with breathing difficulty, dizziness, hypotension, cyanosis and loss of consciousness and may lead to death.

Grade 1 - Mild	Grade 2 - Moderate	Grade 3 - Severe	Grade 4 – Life-threatening	Grade 5- Death
-	-	Symptomatic	Life-threatening	Death
		bronchospasm, with or	consequences; urgent	
		without urticaria;	intervention indicated	
		parenteral intervention		
		indicated; allergy-related		
		edema/angioedema;		
		hypotension		

These tables will be replaced with the CoFAR specific grading system for allergic reactions as displayed below.

Grade 1 - Mild	Grade 2 - Moderate	Grade 3 – Severe	Grade 4 - Life threatening	Grade 5 - Death
Transient or mild	Symptoms that produce	Marked limitation in	Extreme limitation in	Death
discomforts (<48	mild to moderate	activity, some assistance	activity, significant	
hours), no or	limitation in activity	usually required; medical	assistance required;	
minimal medical	some assistance may be	intervention/therapy	significant	
intervention/thera-	needed; no or minimal	required, hospitalization	medical/therapy.	
py required. These	intervention/therapy is	is possible. Symptoms	Intervention is required;	
symptoms may	required.	may include	hospitalization is	
include pruritus,	Hospitalization is	Bronchospasm with	probable. Symptoms may	
swelling or rash,	possible. These	dyspnea, severe	include persistent	
abdominal	symptoms may include	abdominal pain, throat	hypotension and/or	
discomfort or	persistent hives,	tightness with	hypoxia with resultant	
other transient	wheezing without	hoarseness, transient	decreased level of	
symptoms.	dyspnea, abdominal	hypotension among	consciousness associated	
	discomfort/ increased	others. parenteral	with collapse and/or	
	vomiting or other	medication(s) are usually	incontinence or other life	
	symptoms	indicated.	threatening symptoms.	

1 PREFACE

The Statistical Analysis Plan (SAP) for *Oral Desensitization to Egg with Subsequent Induction of Sustained Unresponsiveness for Egg-Allergic Children using Baked Egg or Egg Oral Immunotherapy (OIT)* describes and expands upon the statistical information presented in the protocol. This trial is sponsored by the NIAID and was designed and implemented at NIAID funded CoFAR sites. The Emmes Corporation serves as the SACCC for CoFAR.

This document describes all planned analyses and provides reasons and justifications for these analyses. A listing of tables, listings, and figures planned for the final analyses are provided in a separate document. Regarding the final analyses and Clinical Study Report (CSR), this SAP follows the International Conference on Harmonisation of Technical Requirements for Registration of Pharmaceuticals for Human Use (ICH) Guidelines, as indicated in Topic E3 (Structure and Content of Clinical Study Reports), and more generally is consistent with Topic E8 (General Considerations for Clinical Trials) and Topic E9 (Statistical Principles for Clinical Trials). The structure and content of the SAP provides sufficient detail to meet the requirements identified by the FDA and ICH, while all work planned and reported for this SAP will follow internationally accepted guidelines published by the American Statistical Association and the Royal Statistical Society for statistical practice.

This document contains three sections: (1) a review of the study design, (2) general statistical considerations, and (3) comprehensive statistical analysis methods for efficacy and safety outcomes. Any deviation from this SAP will be described and justified in protocol amendments and/or in the CSR, as appropriate. The reader of this SAP is encouraged to also review the study protocol for details on conduct of the study and the operational aspects of clinical assessments.

2 INTRODUCTION

The overarching goal of this study is to advance the development of safe and effective treatments for egg allergic patients. Previous research has shown efficacy for administration of egg oral immunotherapy (eOIT) in this population. This study compares the efficacy and safety of eOIT vs administration of baked egg in baked egg tolerant participants. The section below provides more detail on the purpose of the analysis.

2.1 Purpose of the Analyses

The purpose of this trial is to assess the efficacy and safety of eOIT compared to baked egg in egg allergic but baked egg tolerant participants. This is an unblinded multicenter randomized trial without a placebo control. Baked egg tolerant participants were randomized to receive either eOIT or baked egg daily. An OFC will be performed at Year 2 to assess desensitization followed by an OFC off-therapy with an open feeding to assess sustained unresponsiveness (the primary efficacy endpoint). In addition, 40 baked egg intolerant participants were enrolled and assigned to eOIT to facilitate comparison of the efficacy and safety of eOIT in baked egg tolerant compared to baked egg intolerant participants. Secondary endpoints address safety and alternate measures of efficacy as well as immunologic comparisons. The timing of the analyses are defined in Section 6.2.

3 STUDY OBJECTIVES AND ENDPOINTS

This section focuses on protocol-specified study objectives (Section 3.1), protocol-specified endpoints (Section 3.2) and operational definitions for those endpoints (Section 3.3). Throughout the SAP, successfully consumed dose (SCD) refers to the cumulative dose consumed without dose limiting symptoms.

Throughout this document, the doses of egg white solid for Egg OIT are given in milligrams of egg white solid, not egg white protein. It is estimated that 1 mg egg white solid is equivalent to approximately 0.70 mg of egg white protein.

3.1 Study Objectives

The primary objective of the study is to determine in baked-egg tolerant, but egg-allergic, children whether daily baked egg therapy vs. daily oral administration of egg white solid escalated to a maximum of 2500 mg/day, increases sustained unresponsiveness as measured by a 7444 mg egg white protein OFC performed 8-10 weeks after therapy discontinuation by the 2 year time point.

Secondary objectives are to:

- 1. Determine the percentage of subjects who can successfully consume without dose limiting symptoms at least 4444 mg egg white protein of a 7444 mg egg white protein OFC after the initial desensitization phase of approximately 1 year of the study and at 2 years.
- 2. Determine the incidence of all serious adverse events.
- 3. Characterize unrestricted egg consumption after conclusion of treatment via long term follow-up.

Tertiary (mechanistic) objectives include testing the following hypotheses:

- 1. The development of clinical sustained unresponsiveness to egg is associated with a reduction in allergen-specific Th2 effector cells, an increase in allergen-specific T regulatory (Treg) cells, and an induction of allergen-specific T follicular helper (Tfh) cells.
- 2. The development of the desensitized state to egg is associated with the down-regulation of basophils.
- 3. The persistence of egg allergy is associated with an epitope-specific IgE antibody profile that is distinct from persons who lose their clinical allergy to egg.
- 4. Sustained unresponsiveness will be associated with a predictive transcriptional signature detectable in whole blood or allergen restimulated PBMCs.

While the above objectives have been framed in terms of the randomized comparison that is central to this study, individuals who comprise the Egg OIT assignment group will have endpoints similar to the randomized cases. The assignment group will be compared to the randomized arms and evaluated for sustained unresponsiveness, desensitization, safety and immune system function. It is anticipated that this group will have less desensitization and sustained unresponsiveness success than the randomized Egg OIT subjects. If supported by the results, it will be an objective to determine if immune parameter studies can help explain the differences.

3.2 Endpoints

The primary clinical efficacy endpoint is the development of sustained unresponsiveness to egg consumption at 2 years as assessed with a 7444 mg egg white protein OFC and open feeding, 8-10 weeks after discontinuing therapy.

The secondary endpoints are as follows:

- The development of desensitization to \geq 4444 mg egg white protein at 1 year and 2 years.
- Incidence of all serious adverse events during the study.
- Changes in egg-specific IgE and IgG4, changes in PST mean wheal diameters, basophil reactivity, CD154+ CD4+ Th2 cells, Tregs, and Tfh cells as described further in Sections 3.3 and 11.
- Unrestricted consumption of unbaked egg as reported on the annual long term questionnaire.

3.3 Study Definitions and Derived Variables

The primary endpoint of the study will be the development of sustained unresponsiveness to a 7444 mg egg white protein OFC followed by open consumption of a whole egg, 8-10 weeks after discontinuing 2 years of daily Baked Egg or Egg OIT. OFCs will be conducted in a supervised setting and safety parameters will be carefully monitored. Individuals off therapy for 8-10 weeks, successfully demonstrating consumption of 7444 mg egg white protein during OFC without dose-limiting symptoms followed by an open feeding of a meal-sized portion of egg are considered successes; those not receiving the open feeding of a meal-sized portion of egg due to site error are also considered successes. Individuals who do not attempt this off therapy OFC or do not successfully consume 7444 mg egg white protein for this off therapy OFC will be considered "failures" with respect to this endpoint.

For the desensitization endpoint, all individuals with an SCD \geq 4444 mg egg white protein will be considered successes All others will be considered "failures" with respect to this endpoint.

For safety endpoints, the pre-defined secondary endpoint is the incidence of serious adverse events. Additional safety endpoints of interest include the incidence of adverse events related to dosing which will be estimated from the dosing symptom logs. For the first 12 months on therapy, or for the time until reaching the maximum maintenance dose if this occurs after 12 months, all dosing symptom logs are required to be submitted. Otherwise, only doses with reactions or missed doses have dosing symptom logs reported in the data system. All non-reported doses are assumed to have been successfully administered without reaction or treatment required. To estimate the number of doses administered, the following algorithm will be used:

Through Week 52: Date of last dose is calculated as the minimum of the completion date of the Week 52 OFC, the drug discontinuation date and the study withdrawal date minus one day. It is assumed that a dose would not occur on the day of Week 52 OFC.

The number of expected doses will be calculated as days from treatment initiation to date of last dose and the percent of doses administered will be calculated as administered doses/expected doses.

After Week 52: For subjects who discontinued dosing or withdrew from the study, the date of last dose is calculated as the minimum of the drug discontinuation date and the study withdrawal date minus one day. For subjects who did not discontinue dosing or withdraw, the date of last dose is calculated as the maximum of the date of last study visit and the day before their Year 2 desensitization OFC. Doses without dosing symptom logs that are to have occurred after 12 months but before the date of last dose are counted as doses that were administered with no symptoms. It is assumed that a dose would not occur on the day of the Year 2 desensitization OFC.

The number of expected doses will be calculated as days from the day after the Week 52 OFC through the discontinuation above. The percent of doses administered will be calculated as administered doses/expected doses.

Derived variables for mechanistic data are as follows:

1. % antigen-specific IgE = (antigen specific IgE / total IgE) X 100

Egg-specific IgG4/IgE: The egg specific IgG4/IgE ratio was calculated by converting IgG4 level from mgA/L to ng/mL and converting IgE level from kUA/L to ng/mL with the formula (IgG4 \times 1000) \div (IgE \times 2.4).

- 2. Activated Basophils = % CD63+ cells
- 3. Frequency and phenotype of egg-responsive T cells:

From 6 hour flow cytometry data:

a. CD154+CD3+CD4+ cell count (per million CD3+/CD4+)

b. CD154+CD3+CD4+(X)+, where X is IL-4, IL-13, IFN-g, IL-10, CCR4, CCR6, or CXCR5:

- 1. Cell count (per million CD3+/CD4+)
- 2. Frequency of CD154+CD3+CD4+, shown as a percentage
- 3. Delta (Egg-Media, CD3/CD28-Media).

c. CD154+CD25+CD127-CD3+CD4+ cell count (per million CD3+/CD4+)

From 18 hour data:

a. CD154+CD25+CD127-Foxp3+CD3+CD4+ cell count (per million CD3+/CD4+)

b. CD154+CD25+CD127-Foxp3+CD3+CD4+(X)+, where X is IFN-g, IL-10, CCR4, CCR6, or CCR9:

- 1. Cell count (per million CD3+/CD4+)
- 2. Frequency of CD154+CD25+CD127-Foxp3+CD3+CD4+, shown as a percentage
- 3. Delta (Egg-Media, CD3/CD28-media)

Effector regulatory ratio (Th2:Treg ratio):

This ratio is defined as CD154+CD3+CD4+IL4+ cell count (from 6h assay)/CD154+CD25+CD127-Foxp3+CD3+CD4+ cell count (at 18h), each adjusted with the same denominator (i.e., per million CD3+CD4+ cells).

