Endpoints and analysis: The primary endpoint of the study will be the development of sustained unresponsiveness to a 7444 mg egg white protein OFC followed by open consumption of a whole egg, 8-10 weeks after discontinuing 2 years of daily Baked Egg or Egg OIT. OFCs will be conducted in a supervised setting and safety parameters will be carefully monitored.

Individuals off therapy for 8-10 weeks, successfully demonstrating consumption of 7444 mg egg white protein OFC without dose-limiting symptoms followed by consuming a whole egg will be considered "successes." All others will be considered "failures" with respect to this endpoint. Among all subjects randomized, the number of subjects on each treatment successfully demonstrating sustained unresponsiveness will be compared to those failing to tolerate this quantity by Chi-square analysis.

Expected outcome/potential limitations: The expected outcome is that 40% of Baked Egg vs. 70% of Egg OIT subjects will tolerate 7444 mg egg white protein OFC, 8-10 weeks after discontinuing Egg OIT or Baked Egg products. The primary limitation to the study is the possibility that we have over-estimated the number of subjects who will tolerate the therapies or subjects do not adhere to dietary restrictions.

Secondary Objectives:

1. Determine the percentage of subjects who can successfully consume without dose limiting symptoms at least 4444 mg egg white protein of a 7444 mg egg white protein OFC after the initial desensitization phase of approximately 1 year of the study and at 2 years.

Rationale: Subjects allergic to egg often have accidental allergic reactions to small amounts of egg in other foods. Generally, the amount of egg causing these accidental allergic reactions is less than 500 mg of egg protein. Previous studies suggest that the continuous administration of a food allergen leads to a "desensitized" state in which an allergic subject will be unresponsive to the ingestion of a food allergen as long as they continue to ingest a small amount of the food on a daily basis.⁸⁰ Food challenges of egg white solid can be done to determine if accidental ingestions of typical amounts of egg could occur without adverse effects.

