At the 2 year time point all subjects will have a 7444 mg egg white protein desensitization OFC on therapy. If the subject fails the 7444 mg egg white protein OFC on therapy, the subject will stop therapy and treatment options will be discussed with the subject. If the 7444 mg egg white protein OFC on therapy is passed, then the subject will be removed from therapy for 8-10 weeks and tested for sustained unresponsiveness with a second 7444 mg egg white protein OFC. If this 7444 mg egg white protein OFC off therapy is passed with successful consumption of an open feeding of egg, the subject will be considered to have achieved sustained unresponsiveness and advised to add egg to their diet on a regular basis and will be followed at 3 months by phone and 6 months in clinic to assess their egg diet history and reactivity to egg. If the subject fails the 7444 mg egg white protein OFC off therapy, further treatment options will be discussed with the subject.

ANNUAL LONG TERM FOLLOW-UP

All subjects will be contacted by telephone at years 3, 4, and 5 (through September 30, 2018) to assess consumption of egg in the diet.

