9.1 Study Endpoint Assessment

9.1.1 Primary Endpoint

The primary endpoint is defined in Section 3.1.1. For the randomized portion of the study an intent-to-treat analysis will be performed. Sustained unresponsiveness can only be demonstrated after discontinuation of active therapy for 8-10 weeks. Individuals successfully demonstrating dose limiting symptom-free consumption of 7444 mg egg white protein by OFC (i.e., dose-limiting symptom-free dosing followed by meal size portion) will be considered successes. All others will be considered to be failures with respect to this endpoint. Analysis will be via the Chi-square test.

9.1.2 Secondary Endpoints

The secondary endpoints are defined in Section 3.1.2.

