4.4.3 Blinding

This study is unblinded.

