7 STUDY PARTICIPANTS

7.1 Participant Disposition

Participant disposition will be described in tables by site and treatment group.

A CONSORT diagram will describe the participant disposition and loss to follow-up through the course of the study.

7.2 **Protocol Deviations**

Participant-specific protocol deviations will be described by individual, treatment group and site. Site specific deviations will be described by site. Listings will include a description of the deviation and any action taken as a result.

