8.3.3 Exploratory Efficacy Analyses

Although not specified in the protocol, changes in SCD from baseline to each protocol OFC are of scientific interest. The change in SCD will be compared between treatment using the Wilcoxon Rank Sum test to do pairwise comparisons between treatment groups. Effects of age will also be explored.

Analyses will also consider participants who successfully passed the desensitization OFCs to 7444 mg of egg white protein at the Week 52 and Year 2 OFCs. Comparisons between groups will be assessed in a similar fashion to the secondary endpoints above.

Clinical and immunological predictors of sustained unresponsiveness are of great scientific and medical interest. Of particular interest is the effect of age on treated effect and clinical outcomes. Logistic regression may be used to identify predictors of clinical response (i.e., desensitization and/or sustained unresponsiveness). Predictors will be incorporated into models adjusting for treatment where possible. Transformations will be implemented as appropriate and model fit will be assessed using the Hosmer-Lemeshow goodness of fit test. Area under the curve (AUC) may be used as an assessment of predictor strength. If the number of successes permits, multivariable models may be fit and stepwise regression techniques applied to identify important predictors or combinations of predictors.

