14 SUMMARY OF CHANGES IN THE CONDUCT OF THE STUDY OR PLANNED ANALYSES

This section will be updated as necessary at the time of analysis or amendment to the SAP.

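### SAP 3.3 and 8.3.1 do not apply the protocol's primary-endpoint rule: feedings omitted through site error count as successes, the catch-all for failures is gone, and no analysis under the protocol rule is planned

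*SAP*

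**What the plan says.** **Protocol.** Section 2.1 describes a success as a child off therapy for 8-10 weeks who consumes the 7444 mg challenge "without dose-limiting symptoms followed by consuming a whole egg will be considered" a success. Section 9.1.1 has the same two-part requirement, with a meal-size portion as the second part, and closes with "All others will be considered to be failures with respect to this endpoint". Section 2.1 has an equivalent closing rule. Section 6.4 (Two Year OFC) says that if the off-therapy challenge "is passed with successful consumption of an open feeding of egg, the subject will be considered to have achieved sustained unresponsiveness"; it requires the feeding but has no catch-all for other outcomes.

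**SAP 3.3.** Success is the passed challenge followed by the open feeding, and "those not receiving the open feeding of a meal-sized portion of egg due to site error are also considered successes". Failure is then defined by two routes only: the off-therapy challenge was not attempted, or the 7444 mg was not consumed. A catch-all for failures does appear in 3.3, but only for the desensitization endpoint.

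**SAP 8.3.1.** The endpoint is first described as the challenge followed by a successful open feeding, with no site-error exception. The next sentence says that the arms are compared on the proportion who pass the Year 2 challenge.

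**Context.** SAP 4.1 treats the open feeding as part of passing. SAP 6.5 points to 3.3 for missing data on the primary endpoint and plans nothing further. SAP 4.4.3 states "This study is unblinded". SAP 14, the record of changes, reads "This section will be updated as necessary at the time of analysis or amendment to the SAP".

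**The concern.** These rules fix the numerator of the primary analysis. A child whose site omitted the feeding is a failure under Protocol 2.1 and 9.1.1 and a success under SAP 3.3. A child who passes the challenge and then reacts to the feeding is a failure under the protocol, falls in neither failure route of SAP 3.3, and would be counted as passing if the comparison sentence of 8.3.1 were programmed as written. Two analysts could therefore derive different numerators from the same data.

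The site-error class is also not defined, and nobody is named to decide it. Because treatment allocation is known, a discretionary route to success should be settled without knowledge of arm and its influence shown. Neither 6.5, 8.3.1 nor 8.3.3 plans a comparison under the protocol's rule. The SAP does mark another departure openly (8.3.3: "Although not specified in the protocol, changes in SCD from baseline to each protocol OFC are of scientific interest"), but the endpoint exception carries no such note and no reason.

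**Working it through.** **1. The rules side by side, for each possible outcome**

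| Outcome at the off-therapy visit | Protocol 2.1, 9.1.1 | SAP 3.3 | SAP 8.3.1, endpoint description | SAP 8.3.1, comparison sentence read literally |
|---|---|---|---|---|
| Challenge passed, feeding eaten | success | success | success | counted |
| Challenge passed, feeding omitted by site error | failure | success | not a success | counted |
| Challenge passed, reaction to feeding | failure | in neither failure route | not a success | counted |
| Challenge passed, feeding refused, unfinished, or missed for another reason | failure | in neither failure route | not a success | counted |
| Challenge failed or not attempted | failure | failure | not a success | not counted |

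Row 2 is a substantive difference between protocol and SAP. Rows 3 and 4 are a drafting conflict: SAP 4.1 and the endpoint description in 8.3.1 show that these children are meant to be failures.

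**2. The plan's own figure**

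Inputs (Protocol 9.3, SAP 5): 40% vs 70%, two-sided 5%, 85% power, 96 randomized 1:1. The pooled-variance formula without continuity correction gives, per arm,

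n = [1.960 × √(2 × 0.55 × 0.45) + 1.036 × √(0.40 × 0.60 + 0.70 × 0.30)]² / 0.30² = (1.379 + 0.695)² / 0.09 = 47.8, so 48 per arm and 96 in total.

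The plan's figure reproduces. Exact enumeration of the uncorrected chi-square at 48 per arm gives power of 85.4%.

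**3. Weight of one child**

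1/48 = 2.1 percentage points of an arm's rate.

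**4. How many reclassified children change the test**

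Planned counts: 0.70 × 48 = 33.6, rounded to 34; 0.40 × 48 = 19.2, rounded to 19. Chi-square = 96 × (34 × 29 − 14 × 19)² / (48 × 48 × 53 × 43) = 9.48, p = 0.0021. Now suppose that k Egg OIT successes, and none in Baked Egg, were site-error cases and became failures:

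| k | Egg OIT vs Baked Egg | p |
|---|---|---|
| 0 | 34 vs 19 | 0.0021 |
| 1 | 33 vs 19 | 0.0041 |
| 2 | 32 vs 19 | 0.0078 |
| 3 | 31 vs 19 | 0.014 |
| 4 | 30 vs 19 | 0.025 |
| 5 | 29 vs 19 | 0.041 |
| 6 | 28 vs 19 | 0.066 |

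Six one-sided reclassifications are needed from the planned result. From an observed 29 vs 19, one is enough.

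**5. Power, with an assumed share m of challenge passers missing the feeding through site error, equal in both arms**

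The documents give no value for m; 1%, 2% and 5% are assumptions. The documents also do not say under which rule 40% and 70% were set, so both readings are shown. In reading A the SAP-rule rates are 40% and 70%, and the protocol rule multiplies both by (1 − m). In reading B the protocol-rule rates are 40% and 70%, and the SAP rule divides both by (1 − m).

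| m | Expected cases, Egg OIT (48 × 0.70 × m) | Expected cases, Baked Egg (48 × 0.40 × m) | A: power, SAP rule → protocol rule | B: power, SAP rule → protocol rule |
|---|---|---|---|---|
| 1% | 0.3 | 0.2 | 85.4% → 84.7% | 86.2% → 85.4% |
| 2% | 0.7 | 0.4 | 85.4% → 83.9% | 87.0% → 85.4% |
| 5% | 1.7 | 1.0 | 85.4% → 81.4% | 89.2% → 85.4% |

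The expected cases are for reading A.

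**6. Type I error**

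With an assumed 55% in both arms and m equal in both, exact type I error is 5.1% under the SAP rule, and 5.1% (m = 2%) or 5.2% (m = 5%) under the protocol rule. A site-error rule that does not depend on arm leaves the test's level essentially unchanged.

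**The case against.** The exception can be defended on its merits. The primary objective (Protocol 2.1, SAP 3.1) measures the outcome by the 7444 mg challenge, and scoring a child who consumed all of it as a failure because staff omitted the feeding is arguably the less faithful choice. The exception is written openly in the section that SAP 6.5 names for missing data. An empty Section 14 is weak evidence of anything, since it is to be completed at analysis or amendment. Omitted feedings should also be visible, because "Participant-specific protocol deviations will be described by individual, treatment group and site" (SAP 7.2). The likely number of cases is small. All of this stands. It removes any case for insisting on the protocol rule as the primary analysis. It does not remove the mismatch between the documents, and a deviation listing does not repeat the primary comparison.

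A reader might go further and infer three things that the documents do not support:

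- *That the exception favours Egg OIT, or was written with outcomes in view.* The SAP describes randomization in the past tense and the trial is open label, but neither document gives the number of cases, their split by arm, or what was known when the rule was set. Relative to the protocol rule, the exception can only leave each arm's rate unchanged or raise it. Which way the difference moves depends on where the cases fall.
- *That restoring the protocol rule costs a fixed amount of power.* This depends on which rule the 40% and 70% refer to. Protocol 2.1 words the expectation as tolerating the challenge, which suggests the SAP-rule reading; Protocol 9.3 calls them sustained-unresponsiveness rates, which suggests the protocol-rule reading. Under the second there is no loss.
- *That the SAP intends to count children who react to the feeding as successes.* SAP 4.1 and the endpoint description in 8.3.1 point the other way.

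**Conclusion.** The point holds. On the primary endpoint SAP 3.3 departs from Protocol 2.1 and 9.1.1, and SAP 8.3.1 does not match SAP 3.3. The site-error exception is a defensible but unexplained change with no analysis under the protocol rule. The missing catch-all and the comparison sentence in 8.3.1 are drafting conflicts that, taken literally, would let a child be scored as a success whom the protocol scores as a failure.

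The expected effect is small: fewer than two cases per arm at an assumed 5% of passers, and six one-sided reclassifications to overturn the planned result. It becomes decisive only if the result lies at the significance boundary. These figures rest on 48 treated children per arm, the uncorrected chi-square and assumed shares; the actual count is not in the documents. Protocol-rule power lies between 81.4% and 85.4% over the assumed 1-5%, depending on which rule the planning rates refer to, so no single power loss should be quoted.

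**What to change.** 1. In SAP 3.3, restore the catch-all for the primary endpoint: everyone not meeting the success definition is a failure. Name explicitly those who react to, refuse or do not finish the open feeding, and those who miss it for any reason other than site error.
2. In SAP 8.3.1, compare the proportions meeting the primary endpoint as defined in Section 3.3, in place of the proportions passing the Year 2 challenge.
3. Either rule may stay primary. Define site error and have it classified without knowledge of arm. Record the exception as a change from the protocol with its reason, and report the number of such children by arm (the 7.2 deviation listing can supply it). Repeat the primary comparison under the other rule as a labelled sensitivity analysis; if the SAP rule stays primary, that is site error counted as failure.
4. Editorial: the feeding is a whole egg in Protocol 2.1 and the first sentence of SAP 3.3, but a meal-sized portion in Protocol 6.6 and 9.1.1 and later in SAP 3.3. Reconcile the wording across these sections.

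The cost is SAP wording and one extra table. Sample size and data collection do not change. If the protocol rule is chosen as primary, a child who consumed the full 7444 mg but was not offered the feeding counts as a failure, and reported rates are lower by 2.1 points per such child in an arm of 48.
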